#### **D. Data analysis and sample size considerations:**

Study data will be collected and managed using REDCap electronic data capture tools hosted at VA CT Healthcare System. REDCap (Research Electronic Data Capture) is a secure, web-based application designed to support data capture for research studies, providing 1) an intuitive interface for validated data entry; 2) audit trails for tracking data manipulation and export procedures; 3) automated export procedures for seamless data downloads to common statistical packages; and 4) procedures for importing data from external sources (Harris et al 2009).

**Data Analysis:** Descriptive statistics will be calculated and normality assumptions will be checked prior to analyses. Transformations or non-parametric methods will be used if normality assumptions are not satisfied. The primary analyses will use linear mixed models (LMMs). LMMs are flexible in modeling the variance-covariance structure of the repeated measures, use all available data on an individual, and provide unbiased and efficient results when data are missing at random. Based on Schwartz Bayesian information criterion (BIC) (smaller is better), we will select the appropriate correlation structure for each dependent variable. Medication will be entered as a categorical variable with two levels (placebo, ALLO 100 nM). Stress/Neutral cues will be entered as a within-subject variable with two levels: stress and neutral. Time will also be a within-subject factor (before cue presentation, and 2 times after each cue presentation). **Specific Primary Aims** will examine the effect of medication on craving (assessed with AUQ), and anxiety (assessed with STAI-6) under stress vs. neutral condition, and stimulant/sedative effects of 40 mg% alcohol. We will consider a significant interaction between medication and stress condition with smaller differences between the stress and neutral conditions on active drug (ALLO) supportive of our hypothesis. **Specific Secondary Aims** will examine the effect of medication, under stress vs. neutral, and in combination with alcohol on

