subjective mood effects, cognitive functioning and motor coordination. As stated in the specific primary aims, a significant interaction between medication and stress condition with smaller differences between the stress and neutral conditions on active drug (ALLO) vs. placebo will be considered supportive of our hypothesis. **Exploratory Aims** will examine the gender-specific effects by adding gender as a between-subject factor in the models above and testing all possible interactions involving gender. All statistical testing for the primary hypotheses will be two-sided at 0.05 significance level. Post-hoc tests and analyses of secondary outcome measures will be adjusted for multiplicity using the Bonferroni correction.

**Sample size considerations:** With 30 subjects per treatment group, we have at least 80% power to detect large effects ( $f=0.5$ ) for the interactions of interest for Aims 1a, 1b, and 1c assuming alpha=0.05. We can also detect large effects for the comparisons of ALLO dose to placebo ( $d= 0.74$ ) under the same assumptions. The effects we are proposing are based on data from Timby et al. 2006 and van Broekhoven et al 2007 who reported that ALLO administration had a large effect ( $d>0.8$ ) on saccadic eye movement and sedation among healthy subjects.

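### Aims 1a and 1b: the named test, medication by stress condition without time, averages in a pre-cue rating where no cue effect can exist and so gives up power

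*Combined protocol and SAP*

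**What the plan says.** All of this stands in section 5 (Research Plan), part D, on data analysis and sample size.

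- **Model.** Linear mixed models are primary. Medication has two levels and cue has two (stress, neutral). "Time will also be a within-subject factor (before cue presentation, and 2 times after each cue presentation".
- **Test.** For the primary aims, the result counted as supportive is a significant interaction of medication with stress condition, with a smaller stress-neutral gap on ALLO. Time is not part of that term, and no other term is named.
- **Alpha.** "All statistical testing for the primary hypotheses will be two-sided at 0.05 significance level".
- **Power.** With 30 per arm, "we have at least 80% power to detect large effects", given as f=0.5, "for the interactions of interest for Aims 1a, 1b, and 1c assuming alpha=0.05". A second sentence adds "We can also detect large effects for the comparisons of ALLO dose to placebo", given as d=0.74. Both are said to rest on published effects above d=0.8 "on saccadic eye movement and sedation among healthy subjects".

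No SD, no correlation between ratings and no definition of f for the repeated-measures model is given.

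**The concern.** The pre-cue rating is taken before the script is presented, so the stress and neutral conditions cannot yet differ because of the cue. ALLO has no cue response to attenuate at that point. A medication by cue term taken over all three ratings therefore gives one third of its weight to a rating where the expected interaction is zero. The estimate shrinks by a third, while its standard error falls only as far as the extra rating reduces noise.

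At stake is the power of the two stress-reactivity hypotheses. The power paragraph does not say which contrast over time its figures describe, so a reader cannot see this loss. A real attenuation could be missed although the data to detect it had been collected.

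**Working it through.** **Inputs.** From part D: 30 per arm, two-sided alpha 0.05, one pre-cue and two post-cue ratings per cue, d=0.74, f=0.5. Assumed: the correlation r between rating times of each subject's stress-minus-neutral difference, taken as 0.3, 0.5 or 0.7; equal variance at each time; the same drug effect at both post-cue ratings; no drug effect on the pre-cue difference.

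**1. The plan's own figures.** With two cue levels, the medication by cue interaction is a two-group comparison of stress-minus-neutral differences. By noncentral t with 58 df and noncentrality d × √(30/2):
- d=0.74: noncentrality 0.74 × 3.873 = 2.87, power 80.5%. The effect giving exactly 80% is d=0.736.
- f=0.5: with two equal groups d = 2f = 1.0, power 96.8%.

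Both sentences reproduce. The d=0.74 figure is the 80% limit (f = 0.74/2 = 0.37), and f=0.5 lies well above it.

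**2. Term as written, averaged over three ratings.** With D the effect at each post-cue rating, in SDs of the difference at one rating, the mean effect is (0 + D + D)/3 = (2/3)D. The SD of the mean is √((1+2r)/3). So d_eff = (2/3)D / √((1+2r)/3).

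**3. Post-cue mean of two ratings.** The mean effect is D and the SD is √((1+r)/2). So d_eff = D / √((1+r)/2).

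**4. Results for D=0.74.**

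| r | d_eff, three ratings | Power | d_eff, post-cue mean | Power |
|---|---|---|---|---|
| 0.3 | 0.493/0.730 = 0.68 | 73% | 0.74/0.806 = 0.92 | 94% |
| 0.5 | 0.493/0.816 = 0.60 | 63% | 0.74/0.866 = 0.85 | 90% |
| 0.7 | 0.493/0.894 = 0.55 | 56% | 0.74/0.922 = 0.80 | 86% |

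The loss is 21, 27 and 30 percentage points. Any gain from using the pre-cue rating as a covariate is not counted.

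**5. The same dilution applied to the plan's interaction effect, f=0.5 (D=1.0).** Three-rating d_eff is 0.91, 0.82 and 0.75; power is 93.5%, 87.5% and 81.0%. The claim of at least 80% survives at each of these correlations. At r=0.9 it would be 74.8%.

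**6. Sensitivity to the number of post-cue ratings.** Table 2 (section 6) lists AUQ and STAI-6 at 0, +15, +20 and +25 minutes in the first condition, which is three ratings after the cue where part D has two. With three post-cue ratings, d_eff for the term as written is (3/4)D / √((1+3r)/4) = 0.81, 0.70, 0.63 for D=0.74, and power is 87%, 76%, 67%. The post-cue mean then has d_eff = D / √((1+2r)/3) = 1.01, 0.91, 0.83 and power 97%, 93%, 88%. The loss is smaller but runs the same way.

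**The case against.** **The two effect sizes are not incompatible.** Because f=0.5 equals d=1.0, a reader might infer that the paragraph contradicts itself. It does not. The figures belong to differently named comparisons, and 96.8% power satisfies a claim of at least 80%. The plan never calls f=0.5 the smallest detectable effect.

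**The interaction power claim is not shown to be false.** A reader might infer from 73%, 63% and 56% that it fails. Those figures start from d=0.74, which the plan attaches to drug versus placebo. From f=0.5, the plan's interaction effect, power stays at or above 81% over the correlations used.

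**The trial is not shown to detect only near-complete abolition of the stress response.** Converting d into percent attenuation needs the size of the placebo stress response, which the documents do not give. Under assumed responses of 0.8, 1.0 and 1.5 SD, a 50% attenuation has 33%, 48% and 81% power, so the conclusion depends wholly on the assumption.

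**The effect-size source is weak.** Saccade and sedation effects in healthy subjects say little about craving or anxiety in AUD. That stands, but it changes no figure here.

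**The model is not fully fixed.** Part D does not say how time enters the test, and the power sentence speaks of interactions in the plural, so a time-specific test may be intended. This is the strongest reply. It does not remove the problem, because the only term named as supportive leaves time out.

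**Aim 1c is outside the argument.** BAES under alcohol follows both cues and has no cue factor. This is correct, and the point is limited to Aims 1a and 1b.

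**Conclusion.** The point holds for AUQ and STAI-6. The named test averages over a pre-cue rating that cannot carry the effect sought, and a post-cue contrast from the same data is materially more powerful: 94%, 90% or 86% against 73%, 63% or 56% when d=0.74 at each post-cue rating.

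The size depends on the assumed correlations, on an equal drug effect at both post-cue ratings, and on equal weighting of the three ratings, which is the plain reading of an interaction without time. If the effect fades by the last rating, both columns fall. This is an avoidable loss of efficiency and an under-specified test. It is not an arithmetic error in the sample size paragraph.

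**What to change.** In part D, for AUQ and STAI-6:

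- Name the tested contrast as the medication difference in the post-cue stress-minus-neutral difference, and say which post-cue ratings enter it, reconciling the count with Table 2.
- Use the pre-cue rating as a covariate instead of averaging it in.
- State power for that contrast: 30 per arm gives 80% power at d=0.74 (f=0.37), in SDs of that difference.
- Give Aim 1c its own named contrast for BAES under alcohol, since it has no cue factor.

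The cost is a re-specified primary contrast, which should be fixed before unblinding, and a rewrite of the analysis and power text. No extra participants, visits or measurements are needed.

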## 6. PROTECTION OF HUMAN SUBJECTS:

Human subjects: Non-treatment seeking individuals with AUD will be recruited from the New Haven area by newspaper advertisements, Craigslist, and flyers. Based on previous human laboratory studies, approximately 10 percent of the subjects who enroll in the study, meet all inclusion/exclusion criteria and are randomized are expected to either drop out or be terminated because of non-compliance with the study procedures. To meet the target sample of 60 completers, a total of 66 participants will be randomized. After the initial phone screening, potential subjects will undergo a comprehensive evaluation that is summarized in Table 1 in “Research Strategy”.

Study Procedures: Table 1 delineates the timeline for study procedures and measures that will be administered at each time point during the laboratory session.

Table 2. Study Procedures (times are approximate)

Time	Measures and Events
Baseline	Urine and BAC check, HR/BP, CIWA, TLFB, AUQ, STAI-6, VAS; BAES, NDS, DES-R, ARCI, SDAS, HVLT-R, Go no-Go, Grooved Pegboard Test, Ghrelin, NPY and ALLO levels, breakfast
-62 min	Ghrelin and NPY levels
-60 min	ALLO infusion starts
-40 min	HR/BP, AUQ, STAI-6, VAS; BAES, NDS, DES-R, ARCI, SDAS, HVLT-R, Go no-Go, Grooved Pegboard Test, ALLO levels
-20 min	HR/BP, ALLO levels
-2 min	Ghrelin and NPY levels
Stress Reactivity Condition 1 (15 min break)	
0 min	Condition 1. (Neutral or Stress) Baseline/Relaxation; BP & HR, AUQ, STAI-6, VAS
+10 min	Image period, BP & HR
+15 min	BP&HR, AUQ, STAI-6, VAS, Ghrelin and NPY levels
+20 min	Recovery period. AUQ, STAI-6, VAS
+25 min	BP&HR, AUQ, STAI-6, VAS, Ghrelin, NPY and ALLO levels

Stress Reactivity Condition 2	
+30 min	Condition 2. (Neutral or Stress). Baseline/Relaxation as described above
+40 min	Image Period as described above
+45 min	BP&HR, AUQ, STAI-6, VAS, Ghrelin and NPY levels
+50 min	Recovery Period as described above
+55 min	BP&HR, AUQ, STAI-6, VAS, BAES, NDS, DES-R, ARCI, SDAS, Ghrelin, NPY, and ALLO levels
Alcohol Infusion	
+70 min	start of IV alcohol infusion
+90 min	Target reached STAI-6, VAS, BAES, NDS, ARCI, SDAS, HVLT-R, Go no-Go, Grooved Pegboard
+118 min	Ghrelin and NPY draw
+120 min	IV alcohol infusion ends, ALLO infusion ends
+150 min	STAI-6, VAS, BAES, NDS, ARCI, SDAS, HVLT-R, Go no-Go, Grooved Pegboard, ALLO levels, Lunch

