**INNOVATION:** This study is among the first to evaluate administration of the neurosteroid ALLO for its effect on craving, anxiety, and subjective stimulant/sedative alcohol effects. Because of its CNS effects and its role in stress, it has a therapeutic potential for those with AUD and comorbidity, particularly PTSD and TBI. The investigators in this study represent a unique collaboration and together are ideally suited to conduct this research. Specifically, we have included experts on neurosteroids and the administration of ALLO ([name]), those who have expertise in alcohol dependence treatment ([name], [name]), neurobiology and laboratory paradigms ([name], [name]), and alcohol administration ([name], [name]). Further, the investigators in this study have extensive expertise in the comorbidity of AUD with PTSD ([name]), and as such are well suited to further study this agent in this patient population. Finally, the study will carefully monitor the safety and effects of ALLO administration alone and in combination with alcohol in AUD, including its subjective effects, its effects on cognition, and on motor coordination.

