**Cognitive functioning:** Little is known about the effects of ALLO on cognitive functioning. However, GABA receptor agonists have been studied extensively and are known to negatively affect cognition. The effects of ALLO on various aspects of memory have been studied in animals and the data show that ALLO impairs spatial, working, and long-term memory [66, 67]. Only one study examined the effects of ALLO administration in healthy women and found that 0.07 mg/kg of ALLO had a statistically significant but relatively minor effect on verbal memory but no effect on semantic or working memory [37]. Verbal memory will be evaluated using *The Hopkins Verbal Learning Test-Revised (HVLT-R)*. The HVLT-R is a word list learning test of verbal memory. The main outcomes for the HVLT-R are percent corrected for immediate and delayed recalls. GABAa agonists have also been shown to affect response inhibition or the ability to suppress a response in rare and irregular situations[68, 69]. We will use the **Go No-Go task** to evaluate response inhibition [70]. A series of rectangles are presented every 1150 ms and participants are instructed to press a spacebar when they see a green rectangle (=go) but refrain from pressing the spacebar when they see a blue rectangle (=no go), and to give equal importance to speed and accuracy. The primary outcome is the number of commission errors. **Motor Coordination:** The negative effects of GABAa agonists on motor coordination have been well documented and studied for decades[71]. Motor coordination will be assessed using the **Grooved Pegboard Test** (Lafayette Instrument Company). This test is a manipulative dexterity test, consisting of a board with randomly positioned slots in which subjects insert pegs. It is an eye-to-hand coordination test that has been used in research studies, including pharmacotherapy studies [72].

**Plasma ALLO:** Deidentified plasma levels of ALLO will be analyzed by [name] lab at UCDavis. Plasma samples will be obtained on multiple time points during the lab session (see Table in Human Subjects section) to examine how levels of ALLO relate to: a) mood, cognitive performance and motor coordination, and b) stress-induced craving and anxiety.

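### The secondary success criterion (medication by stress/neutral) cannot be estimated for the mood scales and the cognitive and motor tests, and those tests' only alcohol-free session on ALLO falls within the loading hour

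*Combined protocol and SAP*

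**What the plan says.** **Criterion.** Section 5.D enters the cue as a within-subject factor with two levels, stress and neutral. For the secondary aims it repeats the primary-aim rule: a significant medication-by-cue interaction, with a smaller stress-neutral gap on ALLO than on placebo, supports the hypothesis. It applies the rule to subjective mood, cognitive functioning and motor coordination. Section 2 assigns DES-R, ARCI and SDAS to mood (Aim 2), HVLT-R and Go/No-Go to cognition (Aim 3a) and Grooved Pegboard to motor coordination (Aim 3b). On the arms, Section 5.D says: "Medication will be entered as a categorical variable with two levels (placebo, ALLO 100 nM".

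**Schedule.** In Table 2 (Section 6), whose heading notes that "times are approximate", ALLO starts at -60 min. The -40 row reads "HR/BP, AUQ, STAI-6, VAS; BAES, NDS, DES-R, ARCI, SDAS, HVLT-R, Go no-Go, Grooved Pegboard Test, ALLO levels", the -20 row "HR/BP, ALLO levels" and the -2 row "Ghrelin and NPY levels". The cue rows carry AUQ, STAI-6 and VAS. The +55 row, after both cues, reads "BP&HR, AUQ, STAI-6, VAS, BAES, NDS, DES-R, ARCI, SDAS, Ghrelin, NPY, and ALLO levels". Alcohol starts at +70 and reaches target at +90.

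**Intent.** The Innovation paragraph (Section 3-4) undertakes to monitor "effects of ALLO administration alone and in combination with alcohol in AUD, including its subjective effects, its effects on cognition, and on motor coordination". Section 2 says levels stabilise after 60 min of infusion. The Overview in Section 5 places the measures of ALLO's own effects in the first hour.

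**The concern.** There are two separate problems.

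1. An interaction between medication and cue needs a stress value and a neutral value of the outcome. If a measure is never taken per cue, the stated criterion has no data behind it. The analyst would have to choose another contrast after the fact, for every instrument named in Aims 2 and 3.

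2. For the three tests, the only result that can speak to ALLO alone is collected while the drug is still being loaded. A small or null difference there could be reported as no impairment at 100 nM, when the exposure at testing was whatever had been reached part-way through the load. The +90 session cannot fill the gap, because alcohol is present.

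**Working it through.** **Step 1: the plan's own figure.** Section 5.D states a detectable ALLO-placebo difference of d = 0.74 with 30 per arm, alpha 0.05 and 80% power. The noncentrality is 0.74 × √(30/2) = 2.87 on 58 df, which gives a two-sided power of 0.805; the exact 80% detectable d is 0.736. The figure reproduces. It concerns the contrast proposed under the fix, before the Bonferroni correction that the plan applies to secondary outcomes.

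**Step 2: where each measure is taken (Table 2).**

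| Row | Min since ALLO start | Alcohol | HVLT-R, Go/No-Go, Pegboard | ARCI, SDAS | DES-R | ALLO level |
|---|---|---|---|---|---|---|
| Baseline | before | no | yes | yes | yes | yes |
| -40 | 20 | no | yes | yes | yes | yes |
| -20 | 40 | no | no | no | no | yes |
| 0 to +50 (cue rows) | 60 to 110 | no | no | no | no | at +25 |
| +55 | 115 | no | no | yes | yes | yes |
| +90 | 150 | at target | yes | yes | no | no |
| +150 | 210 | 30 min after both infusions end | yes | yes | no | yes |

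**Step 3: can the interaction be estimated?** The contrast is (stress − neutral) on ALLO minus (stress − neutral) on placebo. The three tests have no value between 0 and +70. The three scales have one value, at +55, which follows both cues and belongs to neither. The within-person stress-neutral difference is undefined for all six. AUQ, STAI-6 and VAS are rated in both cue blocks, so the interaction can be estimated for them.

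**Step 4: share of the loading dose given.** The load is 191 mcg/kg over 60 min (Section 2).
- At -40: 191 × 20/60 = 63.7 mcg/kg, 33%.
- At -20: 191 × 40/60 = 127.3 mcg/kg, 67%.
- At -2: 191 × 58/60 = 184.6 mcg/kg, 97%.

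**Step 5: plasma level (assumption).** The documents give no kinetic parameters. Suppose one compartment, with the load just reaching the 100 nM plateau held by 57.4 mcg/kg/hr. Then 1 − exp(−k) = 57.4/191 = 0.3005, so k = 0.357 per hour (half-life 1.94 h), and C(t) = 100 × (1 − exp(−kt))/0.3005. This gives 37.4 nM at 20 min and 70.6 nM at 40 min.

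How far this depends on the assumption:
- Two-compartment settings kept only if they stay within 10% of 100 nM from 60 to 180 min give 32 to 60 nM at -40 and 62 to 86 nM at -20. These are extremes of assumed settings, not confidence limits.
- Assuming only 100 nM at 60 min and a rise that never speeds up, the level at 20 min lies between 33 and just under 100 nM.
- One compartment with a maintenance plateau of 100 nM and a half-life of 20 to 40 min gives 166 to 98 nM at 20 min, but 291 to 215 nM at 60 min. That does not fit the plan's statement that levels have stabilised by then.

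**The case against.** The strongest reply concerns the timing. First-hour testing was deliberate, as the Overview shows. ALLO is sampled at -40 and -20, around the likely testing period. The Plasma ALLO paragraph in Section 5.B plans to relate levels to mood, cognition and motor coordination. Aim 3 names no target level, and an ALLO-alone session does exist. All of this stands. The remaining gap is that Section 5.D specifies no model for the exposure analysis, and that no alcohol-free test data are collected after the load.

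A reader might infer three stronger points that the documents do not support:
- *That the tests are done at about half of target exposure.* This follows only from assumed kinetics. The stated times are approximate, the battery's length is not given, and the -40 row prints the scales ahead of the tests, so the tests may run later than -40.
- *That the 100 nM coding is itself an error.* It labels a randomised arm by its target and does not claim that level at every time point.
- *That the tests must be moved.* Late in the hour they would still fall within the load, and they would sit next to the time-0 AUQ and STAI-6 ratings that serve as the pre-cue reference for Aims 1a and 1b. Table 2 also prints a 15-min break in the Condition 1 heading, and its position is unclear.

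On the criterion, one could compare +55 scores between people whose last cue was stress and those whose last cue was neutral, since cue order is random. That is a between-person order contrast, not the within-subject factor that the plan specifies, and it is unavailable for the three tests.

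**Conclusion.** The criterion problem is certain and rests on no assumption: as written, the secondary success rule cannot be computed for any of the six instruments named in Aims 2 and 3. The timing problem is certain as to the clock and the dose: the sole alcohol-free, on-ALLO test session starts with about 33% of the loading dose given, and 67% has been given by -20. The plasma level at that session is unknown from the documents; about 37 and 71 nM hold only under the calibrated one-compartment model. Aim 2 is less exposed, because its scales are repeated without alcohol at +55, after the load and with a level.

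The randomised ALLO-placebo contrasts remain valid, the +90 session still informs ALLO combined with alcohol, and the primary aims are untouched. This is a correction to the analysis and reporting of the secondary aims.

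**What to change.** 1. **Criterion.** For HVLT-R, Go/No-Go, Grooved Pegboard, DES-R, ARCI and SDAS, replace the stress/neutral interaction with the ALLO-placebo difference at each session where the measure is given. Estimate it as the medication effect within session, from a model with session and the Baseline value as covariate. A medication-by-session test should not be the criterion: it asks only whether the effect differs between sessions and would miss a constant one. Keep the alcohol-free sessions (-40 for the three tests; -40 and +55 for the three scales) separate from +90 and +150. Limit DES-R to -40 and +55. Cost: a text change only.

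2. **Reporting.** Describe the -40 cognitive and motor results as obtained during loading, give the measured -40 and -20 levels beside them, and do not present them as the effect at 100 nM. Cost: none beyond samples already planned.

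3. **Optional, for the sponsor to weigh.** Run the three tests later in the existing pre-cue window and add an ALLO tube to the -2 draw. Cost: one more assay per participant (60 completers, 66 randomised), slightly more than the stated 140 ml of blood, and effortful tasks closer to the time-0 ratings. HVLT-R may not fit: Section 5.B says "The main outcomes for the HVLT-R are percent corrected for immediate and delayed recalls", and no delay length is given.

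Separately, the 200-min infusion in the text (60 + 140) and the 180 min in Table 2 (-60 to +120) must be reconciled by the sponsor. Nothing here depends on which is meant.
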